#### 2.1. Analysis Sets

# 2.1.1. All Enrolled Analysis Set

All enrolled analysis set includes all subjects who had signed the informed consent form (ICF) and were enrolled in the study.

# 2.1.2. Safety Analysis Set

The safety analysis set includes all subjects who had signed the ICF and received at least one dose of ImbruvicaTM.

# 2.1.3. Efficacy Analysis Set

The efficacy analysis set will include all subjects who have taken at least 1 dose of study treatment and have both baseline and at least 1 post-baseline efficacy assessment.

#### 2.2. Study Day and Relative Day

Study Day 1 or Day 1 refers to the start of the first study agent administration. All safety assessments at all visits will be assigned a day relative to this date.

Study day or relative day for a visit is defined as:

- Visit date (date of Study Day 1) +1, if visit date is ≥date of Day 1
- Visit date Date of Day 1, if visit date <date of Day 1

There is no 'Day 0'.

# 2.3. Baseline and Endpoint

Baseline is defined as the last non-missing observation on or prior to the start of the first study agent administration.

#### **Primary Endpoint**

• The number and type of TEAEs reported by the investigator or the patient.

#### **Exploratory Endpoints**

- Proportion of subjects experiencing clinical response as per assessment criteria defined in section 9.1 of the protocol.
- Change from baseline in patient-reported outcomes as per EORTC QLQ C-30 and FACIT Fatigue

#### 3. INTERIM ANALYSIS AND DATA MONITORING COMMITTEE REVIEW

For the study no interim analysis and data monitoring committee (DMC) review is planned.

#### 4. SUBJECT INFORMATION

# 4.1. Demographics and Baseline Characteristics

Table 1 presents a list of the demographic variables that will be summarized for the safety analysis set.

**Table 1: Demographic Variables** 

Continuous Variables:	Summary Type	
Age (years)	Descriptive statistics (N, mean, standard deviation [SD], median and range [minimum and maximum]).	
Weight (kg)		
Categorical Variables		
Sex (male, female, unknown, undifferentiated)	Frequency distribution with the number and percentage	
Race (INDIAN)	of subjects in each category.	

#### **Table 2: Baseline Characteristics**

Baseline characteristics	Summary Type
Type of disease	Frequency distribution with the number and percentage
Staging	of subjects in each category.
Number of prior therapies	
ECOG status at baseline	
Number of years of diagnosis	Descriptive statistics (N, mean, standard deviation
EORTC-QLQ-C30 at baseline	[SD], median and range [minimum and maximum]
FACIT Fatigue	
_	

# 4.2. Disposition Information

Number of enrolled subjects and screen failures will be summarized for all enrolled analysis set. The summary table and listing for treatment disposition and study disposition will be presented based on safety analysis set.

The summary for the treatment disposition will be as follows:

- Number of subjects receiving study agent
- Number of subjects who completed the study agent
- Number of subjects discontinued the study agent
- Reasons for discontinuation of study agent

The summary for the study disposition will be as follows:

- Number of subjects receiving study agent
- Number of subjects completed the study
- Number of subjects discontinued from the study
- Reasons for study discontinuation

A listing of subjects will be provided along with the dates, study days and reason for discontinuation/termination for the following categories:

- Subjects who discontinued study agent
- Subjects who terminated study prematurely

# 4.3. Treatment Compliance

Study drug compliance with actual amount taken/expected amount taken X 100% and for categories <80%, 80-<120%,  $\ge120\%$  will be summarized.

#### 4.4. Extent of Exposure

Summary for the total amount of study drug (ImbruvicaTM) received (mg), total treatment duration (month), total amount of study drug prescribed (mg), and the average daily dose (mg/day) will be presented. The average daily dose is calculated as (total amount of study drug received) / treatment duration.

A listing of subject receiving study agent (ImbruvicaTM) along with the start/stop dates, dose amount, frequency, indication and study day will be presented.

Additionally, if dosage reduction/adjustment of ImbruvicaTM is needed, the number of percentages of subjects will be summarized and then date and reason for dose reductions/adjustment will be listed.

#### 4.5. Protocol Deviations

Listing of subjects with major protocol deviations will be provided.

Subjects with major and minor protocol deviations related to Covid-19 (if any) will be listed separately.

A listing of subjects with inclusion/exclusion deviation will be listed, if applicable.

Note If there are a certain number of patients with COVID-19 infection and/or death due to COVID infection during the study, the impact of COVID-19 needs to be assessed. Based on the impact assessments, more listings and summary tables (regarding prior and concomitant, AE, efficacy and etc..) may be added to the analyses.

#### 4.6. Prior and Concomitant Medications

Prior and Concomitant medications will be coded using the latest World Health Organization Drug Dictionary (WHO-DD). Prior medications are defined as any therapy used before the day of first dose (partial or complete) of study agent. Concomitant medications are defined as any therapy used on or after the same day as the first dose of study agent, including those that started before and continue on after the first dose of study agent.

The data on prior and concomitant medications will be listed separately for each subject.

# 4.7. Medical History

[figure not shown]
Medical History will be summarized and listed for all subjects on all enrolled analysis set.

[figure not shown]
## 5. EFFICACY/EXPLORATORY

# 5.1. Exploratory Endpoints

# 5.1.1. EORTC QLQ C-30

European Organization for Research and Treatment of Cancer Quality of Life Questionnaires Core 30.

# 5.1.2. FACIT Fatigue

Functional Assessment of Chronic Illness Therapy-Fatigue

The PRO questionnaires will be collected preferably at the beginning of the clinic visits prior to any procedures or physician interactions

FACIT Fatigue is an instrument for use as a measure of the effect of fatigue in patients with cancer and other chronic diseases. Responses to the 13-item FACIT Fatigue Scale are reported on a 5-point categorical response scale ranging from 0 (not at all) to 4 (very much). Below is the list of items for FACIT-fatigue:

[figure not shown]
[figure not shown]

Figure 1

# 5.1.3. Proportion of subjects experiencing clinical response as per assessment criteria

Following are the response categories to be assessed:

- Complete Response (CR)
- Partial Response (PR)

- Stable Disease (SD)
- Disease Progressive (PD)

Analysis: The number and percentage of subjects will be provided in the following response categories: CR, PR, SD, PD. Data for response assessment will be listed individually for each subject at each visit for efficacy analysis set. The proportion of subjects who achieved the best response of (CR+PR) and its 95% confidence interval (CI) will be analyzed on efficacy analysis set.

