#### **Exploratory Endpoints**

- Proportion of participants experiencing clinical response as per assessment criteria defined in section 9.1
- Change from baseline in patient-reported outcomes as per EORTC QLQ C-30 and FACIT Fatigue

The safety analysis population will include all subjects who sign the ICF and receive at least one dose of ImbruvicaTM. The verbatim terms used by participating physicians to document AEs in the CRF will be coded using the Medical Dictionary for Regulatory Activities (MedDRA). For each adverse event, the percentage of subjects who experience at least 1 occurrence of the given event will be summarized. Adverse events and serious adverse events will be summarized for the study duration by body system, preferred term, intensity, and relationship to ImbruvicaTM using descriptive statistics. Where appropriate, additional summaries, listings, or narratives may be provided for any deaths, serious adverse events, or any adverse events of clinical interest. Changes from baseline to the worst AE grade experienced by a patient during the study will be provided as shift tables. Results of investigations data including vital signs, if any, will be summarized using descriptive statistics.

All subjects who have received at least one dose of ImbruvicaTM and have completed one post-treatment PRO assessment will be considered for exploratory analysis. Exploratory endpoints will be summarized using descriptive statistics. Shift tables will be provided to determine the change in reported outcomes from baseline (Enrolment Visit) until Visit 8 /EOT.

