# 3.1. Overview of Study Design

Relapsed/refractory CLL and MCL patients who have received at least one therapy or CLL patients with deletion 17p selected by investigators and determined to be eligible for ibrutinib treatment as per protocol eligibility criteria will be enrolled in the study. Each subject will receive ibrutinib treatment for a period of 12 months or till disease progression, whichever is earlier. Enrolled subjects will be followed up to 12 months from the treatment initiation. During the study period, data will be collected at monthly intervals for the first 6 months, (monthly visit  $\pm$  7 days; Visit 1 to 6). Subsequent visit would be at 9 months  $\pm$  7 days [Visit 7]. The End-of-Treatment (EOT) visit will be conducted after the completion of 12-months ImbruvicaTM treatment (at Visit 8) or on the day at which the patient discontinued the ImbruvicaTM treatment or study. A telephonic follow-up will be conducted 30 days after the EOT Visit.

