## **Observation Visits (Visit 1 to Visit 8)**

The subjects will be followed up at every monthly interval during Visit 1 to Visit 6 for the first 6 months, followed by seventh visit at month 9 and eighth visit at month 12, and as outlined in the TIME AND EVENTS SCHEDULE The below mentioned procedure and measurements will be performed

- Current medical history (symptoms & signs if any, physical examination including vitals)
- Disease progression assessment
- Compliance Assessment
- Patient-completed PRO instruments (questionnaires and scales)
  - o FACIT Fatigue Instrument
  - o EORTC QLQ-30
- Type, dosage and duration of concomitant medication
- AEs for ImbruvicaTM (see Section
- Investigations (Hematology and coagulation profile); as per TIME AND EVENTS SCHEDULE.

**Note:** Visit 8 or discontinuation visit will be the EOT Visit.

A discontinuation visit is the visit at which the participating physician is discontinuing ImbruvicaTM or first routine clinic visit after the patient stopped taking ImbruvicaTM on his own.

At the discontinuation visit, information on date and reason(s) for ImbruvicaTM discontinuation will be collected, if available. The data for discontinuation visit will be collected on the EOT Visit page in CRF.

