#### 2. GENERAL ANALYSIS DEFINITIONS

The below mentioned general principles will be followed throughout the study:

- The change from baseline is defined as the post-baseline value minus the baseline value. Definition of baseline is provided in section 2.3.
- Descriptive statistics will include number of non-missing subject (n), mean, median, standard deviation (SD), minimum and maximum values for continuous variables, and for categorical variables the frequencies and percentages of subjects will be presented.
- For continuous data, mean and median will be rounded to 1 decimal place more than original data, SD will be rounded to 2 decimal places more than original data and minimum and maximum will be displayed with the same precision as the original data.
- For categorical data, percentages will be rounded to 1 decimal place.
- If a count is 0, the percentage (0%) should not be displayed. The 0 count will be displayed, but the corresponding percentage should be omitted.
- All study data will be included in study data listings. In general, all data will be listed by time point within subject.
- In general, missing data will not be imputed.
- SAS® version 9.4 will be used for all analyses.
- Visit Windows for PRO analysis:

To allow for variation in scheduling, the following set of visit windows will be used to assign evaluations to a most appropriate visit for analysis (Avisit).

Table 1A:

Visit	Avisit	Start Day	Target Day	End Day
SCR/Enrollment visit/Month 1	Screening	-	1	1
Visit 1/ Month 2 (end of month 1)	Month 1	2	30	37
Visit 2/Month 3 (end of month 2)	Month 2	38	60	67
Visit 3/Month 4 (end of month 3)	Month 3	68	90	97
Visit 4/ Month 5 (end of month 4)	Month 4	98	120	127
Visit 5/ Month 6 (end of month 5)	Month 5	128	150	157
Visit 6/ Month 7 (end of month 6)	Month 6	158	180	187
Visit 7/ Month 10 (end of month 9)	Month 9	188	270	277
Visit 8 (end of month 12/End of Treatment)	Month 12	278	360	367

8

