#### **5.1.4.** Progression-Free Survival

Progression-Free Survival (PFS) is defined as the duration from the date of first dose of study drug to either progressive disease the IWCLL criteria or death, whichever occurs first. For subjects who have not progressed and are alive, data will be censored at the Visit 8, or last visit date. The Kaplan-Meier method will be used for descriptive summaries. Median PFS and its 95% CI will be provided. The PFS rates with 95% CI at selected landmark points (6 months and 12 months) will be calculated. PFS will be analyzed on both safety and efficacy analysis set.

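### The CR+PR rate is planned only on the efficacy analysis set, so treated subjects never assessed after baseline drop out of the denominator instead of counting as non-responders

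*SAP*

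**What the plan says.** SAP 5.1.3 fixes the set for the response rate: "The proportion of subjects who achieved the best response of (CR+PR) and its 95% confidence interval (CI) will be analyzed on efficacy analysis set". No other set is named for it.

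SAP 2.1.3 admits a subject to that set after at least one dose, provided they "have both baseline and at least 1 post-baseline efficacy assessment". SAP 2.1.2 defines the safety analysis set as consented subjects with at least one dose, so it contains everyone treated.

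Three further statements bear on the denominator:

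- SAP 5.1.3 on the categories: "The number and percentage of subjects will be provided in the following response categories: CR, PR, SD, PD". None is for subjects who could not be evaluated.
- SAP Section 2 on missing data: "In general, missing data will not be imputed".
- SAP 5.1.4, the next section: "PFS will be analyzed on both safety and efficacy analysis set".

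The protocol synopsis defines its exploratory population differently. Dosed subjects who "have completed one post-treatment PRO assessment will be considered for exploratory analysis".

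On timing, the observation visits in Protocol Section 5 (Visits 1 to 8, the first at Month 1) include "Disease progression assessment". Protocol 3.1 places the end-of-treatment visit at 12 months "or on the day at which the patient discontinued the" drug or study. The Time and Events Schedule marks disease progression assessment at that visit too.

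**The concern.** A response rate is usually read as the share of treated patients who responded. Under the SAP's rule it is the share of treated patients who stayed long enough to be assessed. Those who die or disappear in the first weeks have no recorded response, and removing them can only hold or raise the figure. The SAP treats PFS differently: on the safety set, an early death is a PFS event, yet the same subject vanishes from the response rate one section earlier.

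The second difficulty is the undefined term. 'Efficacy assessment' could mean the disease response assessment, the baseline disease status recorded at enrolment (stage and extent), or a patient-reported outcome. Two programmers could build different sets from the same data.

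At stake is how an exploratory rate is read and compared with other ibrutinib studies. No test and no safety result depends on it.

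**Working it through.** **No planned figure to reproduce.** The SAP gives no expected response rate and no precision target. The 75 subjects come from a committee recommendation (SAP 1.4), not from a formula.

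**Direction.** Let x be the number of responders and m the number of treated subjects with no post-baseline efficacy assessment, all 75 being treated.

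- Efficacy-set rate = x/(75 − m)
- All-treated rate, unassessed counted as non-response = x/75
- Ratio = 75/(75 − m), which is never below 1 and equals 1 when m = 0

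This direction holds for subjects dropped because they lack a post-baseline assessment. A subject dropped for want of a baseline assessment could be a responder, so there the direction is not fixed.

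**How many might be dropped.** The documents do not give m. Disease assessment is due at every visit from Month 1 and at end of treatment, so the gap is mainly death or loss before about Day 30 to 37 (Month 1 plus the 7-day window). Inputs from the Safety Overview in Protocol 1.2: fatal AEs in 9.3% of subjects, during treatment or within 30 days of stopping it; median treatment 8.3 months. Assume an even spread over time.

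- Expected fatal AEs in 75: 75 × 0.093 = 6.98
- Spread over 8.3 + 1 = 9.3 months: 0.74 by Day 30, 0.91 by Day 37
- Spread over 8.3 months: 0.83 by Day 30, 1.02 by Day 37

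So about one early death is expected. The documents give no rate of early loss to follow-up.

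**Effect on the rate.** Responder counts are assumed, and dropped subjects are taken as non-responders. Intervals are exact (Clopper-Pearson) 95%, my choice because the SAP names no method.

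| Responders | All treated | 1 dropped | 2 dropped |
|---|---|---|---|
| 50 | 50/75 = 66.7% (54.8–77.1) | 50/74 = 67.6% (55.7–78.0), +0.9 | 50/73 = 68.5% (56.6–78.9), +1.8 |
| 40 | 40/75 = 53.3% | 40/74 = 54.1%, +0.7 | 40/73 = 54.8%, +1.5 |
| 60 | 60/75 = 80.0% | 60/74 = 81.1%, +1.1 | 60/73 = 82.2%, +2.2 |

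With five dropped, 50/70 = 71.4% (59.4–81.6), a rise of 4.8 points. At the expected numbers above, the Poisson chance of five or more early deaths is 0.1% to 0.4%, so a shift of that size would need early losses or clustered deaths.

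**The undefined term.** Each reading gives a different set:

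- *Response assessment at both times.* None is scheduled at enrolment in the Time and Events Schedule or in the Section 5 enrolment list.
- *Baseline disease status, then response.* The schedule records stage and extent of disease at enrolment, and SAP Table 2 summarises staging. The set can be formed, and subjects without a response assessment drop out.
- *PROs count.* Both questionnaires are scheduled at enrolment and at each treatment visit. A subject with a later PRO but no response assessment stays in the denominator yet fits none of the four listed categories.

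**The case against.** The strongest reply is that little is lost. The SAP reports how many subjects received drug, lists response by subject and visit, lists AEs leading to death, and runs PFS on the safety set. A reader could rebuild the all-treated rate with one division. That is largely right: what is missing is a table row, not information. But the rate and interval that will be quoted are the ones the SAP names.

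Next, restricting to assessed subjects follows the protocol synopsis, and some cited studies report evaluable-only rates. In the phase 1 study, 7 + 23 = 30 responders of 50 evaluable gives 60%. The efficacy-set rate is the like-for-like comparison there, which is a reason to keep it as supportive. The same study enrolled 56, and 30/56 = 53.6%, so the choice of denominator is visible in the protocol's own background.

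Protocol 10.1 keeps the last completed assessment of subjects who stop early. That helps only those who had one.

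Three stronger readings are tempting but not supported:

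- A reader might infer that the baseline requirement can be met only through PROs, because no response assessment is scheduled at enrolment. Stage and extent of disease are recorded then and could serve as the baseline. Only the lack of a definition is established. If PROs do count, the unassessed subject stays in the denominator, which weakens the concern.
- A reader might take the 9.3% fatal-AE or 11.8% AE-discontinuation figures as the share never assessed, giving gaps of several points. Neither is a rate of missing assessments: they cover the whole treatment course, and most such subjects would have been seen at Month 1.
- A reader might add the unstated handling of partial response with lymphocytosis in CLL. That is a separate matter from the denominator. It turns on the response criteria the protocol cites, which are not available here.

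**Conclusion.** The point holds as a minor one. As written, the SAP removes treated subjects with no post-baseline efficacy assessment from the CR+PR denominator, and nothing restores them as non-responders. For those subjects the resulting rate can only equal or exceed the all-treated rate. The term that defines the set is also left open.

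The likely size is about 1 to 2 points, inside an interval about 22 points wide, and zero if every treated subject is assessed. This rests on an even spread of fatal AEs, an assumed responder count, and dropped subjects being non-responders. The even spread is crude, since treatment in the pooled data ran up to 32.3 months, and early losses could add to it. The endpoint is exploratory and descriptive, so neither the primary safety objective nor any test is affected.

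**What to change.** In SAP 5.1.3, report CR+PR with its 95% CI on the safety analysis set. Add a 'not evaluable' row counted as non-response, and keep the efficacy-set rate as supportive. This matches the two sets already used for PFS in SAP 5.1.4.

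In SAP 2.1.3, state which baseline and which post-baseline assessments qualify a subject for the response endpoint, and whether a PRO alone does.

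The cost is a few lines of SAP text and a table row, with no new visits or data. The headline rate may come out slightly lower, by about 1 to 2 points on the assumptions above.

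As an optional and separate suggestion, show the rate for CLL and MCL alongside the pooled figure, since Protocol 9.1 assesses them by different criteria. The intervals within each disease would be wider.

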#### **5.1.4.** Progression-Free Survival

Progression-Free Survival (PFS) is defined as the duration from the date of first dose of study drug to either progressive disease the IWCLL criteria or death, whichever occurs first. For subjects who have not progressed and are alive, data will be censored at the Visit 8, or last visit date. The Kaplan-Meier method will be used for descriptive summaries. Median PFS and its 95% CI will be provided. The PFS rates with 95% CI at selected landmark points (6 months and 12 months) will be calculated. PFS will be analyzed on both safety and efficacy analysis set.

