(defined as single lymph nodes measuring  $\geq 5$  cm). 79% of subjects had at least 1 molecular poorrisk feature. (immunoglobulin variable heavy gene [IgVH] unmutated, del [17p], del [11q], or  $\beta 2$  microglobulin  $\geq 3$  mg/L), with 36% of subjects having del (17p).

The ORR was 67% with 2% CRs. An additional 23% of subjects had >50% shrinkage of lymphadenopathy (nodal response) and 3% had stable disease. The 840-mg cohort was stopped after comparable efficacy and safety between 420 mg and 840 mg was shown. The 12-month PFS estimate for Group 1 was 88% and for Group 3 was 82%.

Study **PCYC-1108-CA** is an ongoing combination CIT Phase 1b/2 study which has completed enrolment. Among 33 subjects with relapsed and refractory CLL/SLL enrolled, 30 have received BR and ibrutinib and 3 have received FCR and ibrutinib. The FCR cohort enrolment was suspended due to slow enrolment related to the lack of subjects at participating sites with relapsed CLL in whom the FCR regimen was considered appropriate. For subjects receiving the BR combination, bendamustine 70 mg/m² was administered on Day 1 and Day 2, combined with rituximab at 375 mg/m² on Day 1 of Cycle 1 and 500 mg/m² on Day 1 for all subsequent courses for a maximum of 6 cycles. Ibrutinib was administered as a continuous daily oral dose of 420 mg. The median number of prior therapies was 2 (range 1 to 4). There were 37% and 13% of subjects, respectively, who were considered either refractory to a purine analogue-containing regimen or to BR (treatment-free interval prior to enrolment was <12 months). Bulky disease was present in 52% of subjects.

At a median follow-up of 4.9 months (range 2.7 to 8.3 months), the ORR was 90% (CR 10%, partial response [PR] 80%). Two additional subjects achieved a nodal response with residual lymphocytosis. Responses appear to be independent of high-risk clinical or genomic features. Ninety percent of subjects currently remain on study. Three subjects have discontinued, 2 for progressive disease (PD) and 1 in pursuit of a stem cell transplant.

Study **PCYC-1109-CA** is an ongoing Phase 1b/2 study combining ibrutinib with ofatumumab. Based on preliminary data from 27 subjects with relapsed or refractory CLL/SLL/prolymphocytic leukaemia (PLL) (n=24) or Richter's transformation (RT, n=3), all subjects achieved a PR (100% ORR). The median follow-up is 6.5 months (range: 5.3 to 10.2 months).

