This is an ongoing multicentre Phase 2 study in subjects with MCL who are relapsed or refractory to their previous treatment. Subjects are stratified based on their previous exposure to the chemotherapeutic agent bortezomib. The objectives include studying the efficacy of ibrutinib given as a continuous fixed dose of 560 mg/day. Preliminary results were recently presented on 68 subjects, of whom 51 were evaluable for efficacy. Overall best response (CR + PR) was 69%—71% among the bortezomib naive subjects (N = 31) and 65% among bortezomib-exposed subjects (N = 20). In some patients, treatment with ibrutinib was associated with a transient increase in peripheral lymphocyte count representing a compartmental shift of cells with the CD19+/CD5+ phenotype from nodal tissues to peripheral blood.

In a single arm ibrutinib monotherapy study conducted in patients with relapsed / refractory MCL an ORR of 67.6% a PFS rate of 63% (95% CI 53, 71%) at 6 months and a duration of response of 17.5 months were observed. In an update on time-dependent outcomes till March 2014, the beneficial effects were sustained. The treatment effect seemed fairly consistent throughout the analysed subgroups, including region, relapsed or refractory disease, bulky disease, number of prior regimens, simplified MIPI score, and prior therapy with bortezomib or lenalidomide.

The benefit- risk balance in the indication "treatment of adult patients with relapsed or refractory MCL" is considered positive, as outstanding activity is shown in terms of high response rate in this patient population of previously treated & relapsed or refractory MCL with an unmet clinical need, along with the added convenience of oral dosing once daily. With these results, ImbruvicaTM (Ibrutinib capsule 140 mg) has been approved in various regions of the world including India in patients with MCL who have received at least one prior therapy.

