# **Treatment Period (Visits 1 to 6 and Visit 7)**

Enrolled subjects will be followed up to 12 months from the treatment initiation. During the study period, data will be collected at monthly intervals for the first 6 months, (monthly visit  $\pm$  7 days; Visits 1 to 6). Subsequent visit would be at 9 months  $\pm$  7 days [Visit 7].

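### SAP 5.1.4 plans one PFS summary across CLL and MCL; with follow-up ending at Month 12, the pooled median is probably not estimable unless MCL is a clear majority, and the pooled rates follow the disease mix

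*SAP*

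**What the plan says.** SAP 5.1.4 defines PFS from first dose to progression or death and uses Kaplan-Meier for descriptive summaries. Three outputs follow. The first is the median: "Median PFS and its 95% CI will be provided". The second is "The PFS rates with 95% CI at selected landmark points (6 months and 12 months) will be calculated". The third is the choice of populations: "PFS will be analyzed on both safety and efficacy analysis set". For subjects alive and without progression, "data will be censored at the Visit 8, or last visit date". SAP 1.2 fixes the horizon: "Enrolled subjects will be followed up to 12 months from the treatment initiation".

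Neither document plans PFS, or any other efficacy output, by disease. Type of disease appears only as a row in SAP Table 2 (baseline characteristics). No CLL:MCL mix is stated or targeted. The registry tables in protocol 1.2 count lymphoid leukaemia and non-Hodgkin lymphoma as a whole, so a mix cannot be derived from them.

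The protocol's background gives PFS for each disease. For CLL/SLL (relapsed or refractory; Group 1 at 420 mg, Group 3 at 840 mg): "The 12-month PFS estimate for Group 1 was 88% and for Group 3 was 82" percent. For MCL: "a PFS rate of 63% (95% CI 53, 71%) at 6 months".

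**The concern.** A Kaplan-Meier median can be read only if the curve falls to 50% within follow-up. On the protocol's cited figures, CLL is far from that at Month 12 while MCL may be past it. One curve for both diseases then gives a median whose existence depends on how many MCL subjects happen to be enrolled. The landmark rates from that curve can be estimated, but they too move with the mix, so they describe neither disease and cannot be set beside the disease-specific figures in protocol 1.2. The amendment history says PFS was added in SAP version 2.0 to give sufficient information on the assessment criteria. An unreached pooled median and mix-dependent rates do that poorly.

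**Working it through.** The plan gives no PFS median, event count or precision target, and N = 75 is a committee recommendation (SAP 1.4). There is therefore no stated figure to reproduce. The question is what MCL share, w, the pooled median needs.

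**Inputs.** CLL 12-month PFS c = 0.88 or 0.82 and MCL 6-month PFS 0.63 (0.53 to 0.71), all from protocol 1.2; N = 75; horizon 12 months. Assumptions: constant hazard within each disease, and w varied because the plan is silent.

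**Each disease alone.**
- MCL 12-month PFS = 0.63² = 0.397; over the interval, 0.53² = 0.281 to 0.71² = 0.504.
- MCL median = 6 × ln 0.5 / ln 0.63 = 9.0 months (6.5 to 12.1 over the interval).
- CLL median = 12 × ln 0.5 / ln c = 65 months at 0.88 and 42 months at 0.82.

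**Pooled 12-month PFS.** S(12) = w × S_MCL(12) + (1 − w) × c. Setting S(12) = 0.5 gives w = (c − 0.5) / (c − S_MCL(12)).

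| MCL 6-month PFS | w needed, c = 0.88 | w needed, c = 0.82 |
|---|---|---|
| 0.53 | 0.38/0.599 = 63% | 0.32/0.539 = 59% |
| 0.63 | 0.38/0.483 = 79% (59 of 75) | 0.32/0.423 = 76% (57 of 75) |
| 0.71 | above 100% | above 100% |

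**Other assumptions, MCL 6-month PFS held at 0.63.**
- Weibull hazard in MCL: falling, w = 80 to 83% (shape 0.9) up to 99% (shape 0.6); rising, 68 to 71% (shape 1.2).
- Horizon of 13 months: 70 to 74%.
- Cross-check from the other MCL figures in protocol 1.2, a 67.6% response rate and "a duration of response of 17.5 months were observed", assuming response at 2 months: 0.676 × exp(−ln 2 × 10/17.5) = 0.455 at 12 months, so w = 88 to 89%.

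**How the pooled rate moves with the mix (c = 0.88).** At 20% MCL: 0.2 × 0.397 + 0.8 × 0.88 = 78%. At 60% MCL: 0.6 × 0.397 + 0.4 × 0.88 = 59%.

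**Simulation.** 10,000 trials of 75, no dropout, log-log limits. Each pair is c = 0.88 / c = 0.82.

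| MCL share | Median reached | Upper 95% limit reached |
|---|---|---|
| 20% | 0% / 0% | 0% / 0% |
| 40% | 0% / 0.2% | 0% / 0% |
| 50% | under 1% / 2% | 0% / 0% |
| 60% | 4% / 11% | under 0.1% / under 0.1% |
| 70% | 19% / 30% | 0.1% / 0.5% |
| 80% | 55% / 63% | 3% / 5% |

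An assumed 15% dropout leaves these roughly unchanged (at 80% MCL, 54% / 62% for the median).

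**MCL alone, 10 to 45 subjects.** At 63% the median is reached in about 79 to 93% of trials, but its upper 95% limit in only about 13 to 35%. If the true 6-month rate is 71%, the median is reached in roughly half of trials (48 to 62%) and the upper limit in 6% or fewer.

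**The case against.** The strongest reply is that 5.1.4 already contains the usable outputs. The 6- and 12-month rates need no median, and an unreached Kaplan-Meier median is an ordinary descriptive result. Nothing in the SAP ranks the median above the landmark rates, so a reader who infers that the main PFS result will be lost goes further than the text allows. This stands.

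The reply also has force on the numbers. The protocol gives no 12-month or median PFS for MCL; both are extrapolated here from one 6-month rate. A reader might take four in five as a fixed threshold, but the documents support only a range, from about 59% MCL to unreachable. It is equally tempting to say that the plan omits a fully estimable MCL median. That is not supported: the point estimate is likely at 63%, but its interval would usually lack an upper limit.

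Finally, the consequence is limited. The study tests no hypothesis, its primary endpoint is treatment-emergent adverse events, PFS is not in the SAP's list of exploratory endpoints, and N was not sized on it. Neither document plans a PFS comparison with the cited trials. All data are listed by subject, so a disease split could be recovered.

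What the reply does not answer is the mix. Landmark rates from a pooled curve vary with it as much as the median does, and listings do not replace a planned by-disease estimate.

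**Conclusion.** The concern holds as a modest, inexpensive improvement. With follow-up to Month 12 and the protocol's cited PFS figures, the pooled median needs a clear MCL majority in every scenario tried: about 76 to 79% at the point estimates and no lower than about 59%. At half MCL or less it is reached in at most about 2% of simulated trials. Because no mix is stated, it will probably be not estimable, though this depends on who is enrolled. The pooled 12-month rate shifts by about 19 percentage points (78% to 59%) between 20% and 60% MCL with no change in either disease.

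The result rests on constant hazards, on the cited trials resembling this population, and on the SAP's silence meaning that the diseases are pooled. The documents do not support the inference that the primary safety objective is affected, or that the plan has no estimable PFS output.

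**What to change.** In SAP 5.1.4:

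- Present Kaplan-Meier PFS separately for CLL and MCL, with the 6- and 12-month rates and 95% CIs as the main estimates in each.
- Give a median only where that disease's curve reaches 50% within follow-up; otherwise report it as not estimable. State in advance that the upper limit for MCL will usually be missing.
- Reconcile the progression definition. Section 5.1.4 names only the IWCLL criteria, whereas SAP 1.1 and protocol 2.1.1, 9.1 and 12.3.1 use the revised lymphoma criteria for MCL. A separate MCL curve needs this settled first.
- Keep the pooled curve, if wanted, as a secondary display with the CLL and MCL counts beside it.

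The cost is SAP wording and a disease split of one table and figure, with no new data collection. The downside is wider intervals within each disease than for the pooled curve.
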